at a dosage of 2 million cells per 1 kg of patient weight (1 intravenous injection, 3 intrathecal with an interval of 5-7 weeks). Group 2 consisting of 9 patients receiving the injections of mononuclear cord blood cells at a dosage of 2 million cells per 1 kg of patient weight and mesenchymal stem cells at a dosage of 1 million cells per 1 kg of patient weight (2 intrathecal and intramuscular injections and 2 intrathecal injections solely). Patients of Groups 1 and 2 received standard rehabilitation therapy. Group 3 consisted of 14 patients receiving standard rehabilitation therapy. The evaluation was conducted 24 weeks after the course of injections. During the treatment, all patients had normal and stable vitals. At the periods of injections or period after them. No allergic or immunological reactions were observed in any patient. There were no deviations from the normal ranges or significant changes in the laboratory indicators of the liver and kidneys functioning, in comparison with the initial level (ALAT, ASAT, bilirubin, urea, and creatinine). Evaluation of the psychological status was made on the CARS scale. The total CARS score was significantly reduced in the Group 2 (a decline of 37.9%); in Group 1, the indicator decreased by 20.0%; in Group 3, i.e. the control group, the indicator decreased by 13.7%. The initial CARS score indicator in each group was at the level of 45. In Groups 1 and 2, there were improvements in behaviour defined for the "Attitude to people", "Body use", "Visual response", "Taste, smell, the reaction on touch and use" and "General Impressions" sub-scales. Those changes were not observed in the control group. The research study proved the safety and effectiveness of the use of cord blood mononuclear cells in the complex treatment of patients. (Transplantation of human cord blood mononuclear cells and umbilical cord-derived mesenchymal stem cells in autism Yong-Tao Lv, Yun Zhang, Min Liu,¹ Jia-na-ti Qiuwaxi,² Paul Ashwood,³ Sungho Charles Cho,⁴ Ying Huan,¹ Ru-Cun Ge,¹ Xing-Wang Chen,¹ Zhao-Jing Wang,² Byung-Jo Kim,⁵ and Xiang Hucorresponding).

\

CLINICAL PURPOSES

Estimation of the safety and efficiency of the method of transfusion of umbilical blood hemopoetic cells to patients with diagnosed autism spectrum disorder without depending on the degrees of compatibility of donor and recipient.

TASKS

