1. Develop an algorithm for using the method of transfusion of hematopoietic umbilical cord blood cells in the treatment of patients with autistic type disorder.
2. To formulate criteria for the selection of patients for this technique.

3. To analyze the efficacy and safety of transfusion of hematopoietic cord blood cells in patients with autistic type disorder using rating scales.
4. Introduce the method of transfusion of cord blood hematopoietic cells to patients with autistic type disorder in the complex therapy of patients with autistic type disorder.

OBJECT OF STUDY

The protocol for testing the method will be carried out on 10 patients with autism spectrum disorder by transfusion of hematopoietic cord blood cells. As a control group, 10 patients with a similar pathology will be examined, comparable in age, gender and degree of autistic disorder according to the “paracopy” type against the background of standard therapy.

Type of study: interventional, prospective, non-randomized with a control group.

Patient selection criteria (indications for this type of treatment):

- age of the patient is from 3 to 15 years.
- Diagnosis: autistic disorder.
- Systemic speech underdevelopment
- The presence of attention deficit hyperactivity disorder as a comorbid state
- Cognitive impairment

Patient exclusion criteria (contraindications for this type of treatment):

- The patient's under 3 years, after 15 years;
- The presence of organic pathology of the brain according to CT, MRI
- The presence of the following diseases in the anamnesis: heart failure in the stage of decompensation, a history of stroke less than 1 year ago, anemia and other blood diseases;
- Decompensation of chronic and endocrinological diseases;
- Acute respiratory viral and bacterial infections, period less than 1 month after the acute phase.
- HIV infection, hepatitis B and C.
- Cancer, chemotherapy and history of cancer;
- Tuberculosis.
- Severe form of intellectual disability as a concomitant disease (diagnosis can be ignored, according to the decision of the Medical Committee of the Center);
- Cerebral palsy.
- Increased convulsive readiness, epilepsy.

Indications and contraindications to this type of treatment for each patient are determined at a consultation of doctors with the participation of a paediatrician or a psychologist (psychiatrist), and transfusiologist.

Research methods

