Evaluation scales CARS, ATEC (to assess the dynamics). Neuropsychological examination, examination of a speech therapist-pathologist. Assessment of neurological status. Determination of the immune status by flow cytometry (CD3; CD4; CD8; CD19; CD16-56). Determination of the level of cytokines in peripheral blood: interleukin 1 beta, interleukin 6, tumor necrosis factor alpha, interleukin 8, gamma interferon. Determination of the HLA genotype of the subject parents and siblings.

The results will be statistically processed using parametric and non-parametric statistics methods using STATA version 9.0, Statistica for Windows version 6.0 and MS Office Excel 2007. Changes from the start of therapy and after 1, 2, 6, 12 months will be compared using the Wilcoxon criterion, comparing data between the main group and the control group using non-parametric method, using the Mann-Whitney test (data are presented in Me - median format with an indication of 25% (q1) and 75% (q3) quartile.

Treatment protocol

Selection of patients and assessment of their psychological status, transfusion of umbilical cord blood HSC in the conditions of day hospital is carried out by specialists of the State budgetary institution of public health "Samara Regional Children's Clinical Hospital N.N. Ivanova Laboratory examination, selection of biomaterial will be carried out by the State Budgetary Institution "MC Dynasty".

Stage 1 - selection and examination of the patient, determination of indications and contraindications to this method of treatment is carried out by a child neurologist, pediatrician (pediatrician), medical psychologist. Assessment of autism disorder is carried out according to the assessment scales of CARS, ATEC.

A prerequisite for inclusion:

- diagnosed with autism spectrum disorder by a psychiatrist,
- Dispensary supervision by a child psychiatrist at the place of residence.

Mandatory general clinical trials (clinical and diagnostic laboratory):

- a) General clinical blood tests (erythrocytes, hemoglobin, platelets, clotting time, leukocytes + formula, COE) - shelf-life 14 days.
- b) general clinical urine test - shelf life 14 days.
- c) feces per helminth eggs - shelf life 14 days.
- d) blood type and rhesus factor.

A patient who meets the selection criteria and has no contraindications for this type of treatment enters into a protocol and signs an informed consent (or his/her legal representative).

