Evaluation of the effect is carried out using the scales used in the introduction to the protocol, evaluation of the neurological and psychological status of the patient.

Evaluation of immune status indicators is carried out 6 months after the last injection.

Cytokine profile is assessed 1, 2, 3 months after the first injection.

Expected results:

It is assumed that transfusions of hematopoietic cord blood cells in patients with autism spectrum disorders will not cause adverse reactions and complications (safe) and will lead to improved social interaction and communication of patients, increased social adaptation, reduced stereotyping, increased self-service skills, increased cognitive functions.

STATISTICAL CONSIDERATIONS

This study will enroll autistic children age 3 to 15 years of age.

Participants will be carried out on 10 patients with autism spectrum disorder by transfusion of hematopoietic cord blood cells. As a control group, 10 patients with a similar pathology will be examined, comparable in age, gender and degree of autistic disorder according to the “paracopy” type against the background of standard therapy.

This is interventional, prospective, non-randomized with a control group study with three intravenous allogeneic, unrelated CB infusion in children ages 3-15 years with ASD/

The primary outcomes will be assessed 1, 2,3,6 and 12 months after the initial infusion in the sequence. Duration of study participation will be 12 months from the time of baseline infusion.

Accrual

It is estimated that up to 2-3 research participants will be enrolled each week and that approximately 4 weeks of accrual will be necessary to enroll 10 participants.

Study Duration

Research participants will be followed for safety for 12 months after the third study infusion.

Demographics and Baseline Characteristics

Demographics and baseline characteristics will be summarized for all research participants. Characteristics to be examined include age, sex, and baseline behavioral status (ATEK).

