The results will be statistically processed using parametric and non-parametric statistics methods using STATA version 9.0, Statistica for Windows version 6.0 and MS Office Excel 2007. Changes from the start of therapy and after 1, 2, 6, 12 months will be compared using the Wilcoxon criterion, comparing data between the main group and the control group using non-parametric method, using the Mann-Whitney test (data are presented in Me - median format with an indication of 25% (q1) and 75% (q3) quartile.

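### The plan specifies tests, medians and quartiles, but no between-group effect estimate or confidence interval, in a 10 v 10 comparison with low power for the closer of its two cited effects

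*Combined protocol and SAP*

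**What the plan says.** CLINICAL PURPOSES gives the aim as "Estimation of the safety and efficiency of the method of transfusion of umbilical blood hemopoetic cells to patients with diagnosed autism spectrum disorder". TASKS words it as "To analyze the efficacy and safety of transfusion of hematopoietic cord blood cells in patients with autistic type disorder using rating scales".

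OBJECT OF STUDY and STATISTICAL CONSIDERATIONS set 10 infused children against 10 controls. The design is stated as "Type of study: interventional, prospective, non-randomized with a control group".

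The analysis text is the same in Research methods and in the last paragraph of STATISTICAL CONSIDERATIONS. It refers in general terms to parametric and non-parametric methods, then names two tests. The Wilcoxon test is for change from the start of therapy. The other is described as "comparing data between the main group and the control group using non-parametric method, using the Mann-Whitney test". Of presentation it says only "data are presented in Me - median format with an indication of 25% (q1) and 75% (q3) quartile".

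No between-group effect measure, confidence interval, significance level, SD, power or rationale for the sample size appears anywhere.

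**The concern.** A median with quartiles describes the spread among children within one group. It does not say how far apart the groups are, allowing for sampling error. A Mann-Whitney test says whether the groups differ detectably, not by how much. A reader of the planned output could subtract one group median from the other for a rough contrast, but would have no measure of its precision.

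With 10 children per group, that precision decides what can be concluded. Two misreadings are possible:

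- A non-significant between-group test could be taken as evidence of no effect when the data are compatible with both no effect and the effect seen in the cited study.
- A significant within-group Wilcoxon test in infused children could be taken as benefit when most of the change also occurs in controls.

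A between-group estimate with its interval guards against both.

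**Working it through.** **Inputs from the documents.** Group sizes are 10 and 10. The background describes a 2011 study with baseline CARS of about 45 in each group. CARS fell by 20.0% with mononuclear cells, 37.9% with mononuclear plus mesenchymal cells, and 13.7% in controls.

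**Assumptions.** The documents give no SD of CARS change, so a range of 2 to 10 points is used. Also assumed are a two-sided 5% level, normal data with equal SDs, unpaired groups and no dropout. The plan gives no sample-size calculation to reproduce, so 10 v 10 is taken as given.

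**Step 1: cited gaps in points.**

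- Mononuclear cells alone: 45 × (0.200 − 0.137) = 2.835
- Mononuclear plus mesenchymal cells: 45 × (0.379 − 0.137) = 10.89

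**Step 2: power of one Mann-Whitney test.** The exact two-sided test at 10 v 10 rejects if U ≤ 23 or U ≥ 77 (actual level 0.043; adding U = 24 would raise it to 0.052). Results are from 40,000 simulated trials per cell.

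| SD of change (assumed) | Power, gap 2.8 | Power, gap 10.9 |
|---|---|---|
| 2 | 81.5% | 100% |
| 3 | 47% | 100% |
| 4 | 29% | 100% |
| 5 | 20% | 99% |
| 6 | 15% | 95% |
| 8 | 10% | 77–78% |
| 10 | 8% | 58% |

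As a check, the normal approximation is power = Φ(d / (SD × √(2/n)) − 1.96). At d = 2.835, SD = 6 and n = 10 this is Φ(2.835 / 2.683 − 1.96) = Φ(−0.90) ≈ 18%. That is slightly above the rank test, as expected.

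For the 2.8-point gap, power drops below 50% once the SD exceeds about 2.9. For the 10.9-point gap, this happens only above an SD of about 11.

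**Step 3: what an interval would add.** The Hodges-Lehmann interval that matches this test runs from the 24th to the 77th of the 100 ordered pairwise differences. Its simulated coverage is about 96%. If the true gap is 2.8 points (positive meaning a larger fall in infused children):

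| SD (assumed) | Typical half-width | Median lower and upper limits |
|---|---|---|
| 4 | 3.9 | −1.1 to 6.8 |
| 6 | 5.9 | −3.1 to 8.7 |
| 8 | 7.8 | −5.1 to 10.7 |

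Among non-significant trials at SD 4 to 8, the interval still reaches 2.8 points or more in 97–98%. It would show the result to be inconclusive, which the test alone does not.

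**Step 4: within-group tests.** The cited falls are 45 × 0.200 = 9.0 points with mononuclear cells and 45 × 0.137 = 6.2 in controls. The exact Wilcoxon signed-rank test with n = 10 would be significant in 98% of infused groups and 81% of control groups at SD 6, and in 87% and 57% at SD 8. A significant fall in the infused group is therefore likely even when most of it is shared with controls.

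**The case against.** **The plan does not exclude an estimate.** It refers to parametric methods without specifying them, and it never says that p-values are the only output. This stands: one cannot say that the plan produces only medians and p-values. What can be said is that no effect estimate or interval is specified.

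**The purpose may not conflict with the analysis.** A reader might infer a contradiction from the word for estimation in CLINICAL PURPOSES. The parallel wording in TASKS suggests that it may simply mean evaluation, so the documents do not support a contradiction. The gap remains, because judging efficacy also needs the size and precision of the difference.

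**The low-power figure is selective and conditional.** A reader might infer that a true effect of the cited size would usually be reported as no difference. Two effects are cited, and the larger would usually be detected. Even for the smaller, the statement needs an SD above about 2.9, and the documents give no SD. The mononuclear-only arm is the closer comparator because this trial gives no mesenchymal cells, but its dose, route and schedule differ from those planned here. The protocol uses neither gap as a design effect.

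**Nothing says that non-significance will be read as no effect.** This stands; it is a risk, not a rule of the plan. The opposite error is at least as plausible, given the within-group tests and the improvement already assumed under Expected results. The power figures also cover one test on one scale at one visit, whereas CARS and ATEC are both assessed repeatedly.

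**An interval can give false assurance.** It does not address confounding in a non-randomized comparison. Controls are to be comparable in age, gender and severity. If that means individual matching, an unpaired interval is miscalibrated: with a within-pair correlation of 0.5, a simulation gave about 99% coverage instead of 95%. Both points stand and shape the fix.

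**Conclusion.** The concern holds in a limited form. The plan specifies no between-group effect estimate or confidence interval, so as written it does not show the size or precision of the treatment difference. That much rests on the text alone.

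The size of the problem rests on assumptions. For the 2.8-point gap, a single Mann-Whitney test has power of about 29%, 15% or 10% at assumed SDs of 4, 6 or 8; at SDs of 2 and 3 it is much higher. The 10.9-point gap would usually be detected (95% at SD 6, about 78% at SD 8).

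The documents do not support saying that the p-value will almost always be uninformative. Nor would an interval always leave zero in play: it excludes zero in just those trials where the matching test is significant. The supportable conclusion is that two misreadings are possible, and that a small addition to the plan guards against both.

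**What to change.** In Research methods and in the last paragraph of STATISTICAL CONSIDERATIONS:

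1. For each between-group comparison, report the Hodges-Lehmann difference in change from baseline (infused minus control) with its 95% confidence interval from the planned Mann-Whitney ranks. State which direction is benefit. If controls are individually matched, use the paired version.
2. Interpret efficacy from this between-group estimate and interval, not from the within-group Wilcoxon tests. State that a non-significant result will not be reported as absence of effect.
3. State that the interval reflects sampling error only and does not account for confounding from non-randomized allocation.

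The cost is a few sentences and a little more output. No new data are needed, and the planned tests are unchanged. The downside is several unadjusted intervals across scales and visits, which must be labelled as descriptive.
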